MACE	Major adverse cardiovascular events
MCV	Mean Corpuscular Volume
mg	Miligram
MI	Myocardial infarction
MKD	Mevalonate Kinase Deficiency
mL	Mililiter
MRI	Magnetic Resonance Imaging
NSCLC	Non-small cell lung cancer

Novartis Amended Protocol Version 03 (Clean) Confidential

OS	overall survival
PD	Pharmacodynamics
PK	Pharmacokinetics
PHI	Protected Health Information
PPS	Per protocol set
PRO	Patient-Reported Outcome
PT	Prothrombin Time
PTS	Post treatment surveillance
q3w	Every 3 weeks
QFT-PLUS	QuantiFERON®-TB Gold Plus assay
QLQ	Quality of Life Questionnaire
QoL	Quality of Life
R0	Completely resected
RDE	Recommended dose for expansion
REB	Research Ethics Board
RNA	Ribonucleic Acid
R Value	ALT/ALP in x ULN
SAE	Serious Adverse Event
SAP	Statistical Analysis Plan
S.C.	Subcutaneous
SJIA	Systemic Juvenile Idiopathic Arthritis
SS	Survival Status
SST	Serum Seperating Tube
SUSAR	Suspected Unexpected Serious Adverse Reaction
T1D	Type 1 Diabetes
Т3	Triiodothyronine
T4	Thyroxine
TBIL	Total bilirubin
TNF	Tumor Necrosis Factor
TRAPS	Tumor Necrosis Factor Receptor Associated Periodic Syndrome
TSH	Thyroid-Stimulating Hormone
UICC	Union for International Cancer Control
ULN	Upper limit of normal
VES	Visit Evaluation Schedule

Glossary of terms

Assessment	A procedure used to generate data required by the study
Biologic Samples	A biological specimen including, for example, blood (plasma, serum), saliva, tissue, urine, stool, etc. taken from a study subject or study subject
Control drug	A study treatment used as a comparator to reduce assessment bias, preserve blinding of investigational drug, assess internal study validity, and/or evaluate comparative effects of the investigational drug
Cohort	A group of individuals who share a common exposure, experience or characteristic, or a group of individuals followed-up or traced over time
Cycles	Number and timing or recommended repetitions of therapy are usually expressed as number of days (e.g.: q28 days)
Discontinuation from study	Point/time when the subject permanently stops receiving the study treatment and further protocol required assessments or follow-up, for any reason. No specific request is made to stop the use of their samples or data.

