6.3 Dose modifications

6.3.1 Dose modification and dose delay

For subjects who do not tolerate the protocol-specified dosing schedule, dose interruptions are either recommended or mandated in order to allow subjects to continue the study treatment. **There are no dose reductions allowed in this study.**

These dose modifications are summarized in Table 6-2. If mandatory dose interruptions are not performed, deviations will be noted. Permanent treatment discontinuation is mandatory for specific events indicated as such in Table 6-2 or listed in Section 7.1.4.

Scheduled dosing of study drug may, at the discretion of the Investigator, be delayed by up to 7 days if subjects present with conditions that require withholding of study drug, e.g., presence of skin ulcer or evidence for active infection (treated or untreated). Outside of this 7 day window, the dose will be considered missed. After a dose is missed, the subject should resume treatment on the original schedule of study drug administration per C1D1. If a subject requires a dose interruption of greater than 42 days from the intended day of the next scheduled dose,

then the subject must be discontinued from the study. Subjects who discontinue the study for a study related adverse event or an abnormal laboratory value must be followed as described in Section 7.1.4.

Infections

Infections are the most common adverse event and may be related to study medication. Subjects should be followed closely for any signs or symptoms of infection and receive prompt appropriate treatment for any suspected infection. Respiratory infections are common in subjects who have had lung cancer, in part due to underlying lung diseases such as chronic obstructive pulmonary disease and other smoking or second-hand smoke related lung diseases. Subjects will have a urinalysis performed at every study visit (screening and throughout the study treatment); occult urinary tract infections, if not promptly treated may result in urosepsis. Site personnel should be aware of this concern and review urinalysis results and take action if treatment of the subject for a urinary tract infection is required.

Novartis	
Amended Protocol Version 03 (Clean)	

Table 6-2 Criteria for dose interruption and re-initiation of treatment for adverse drug reactions

Dose Schedule modifications for Canakinumab ^a	
Worst toxicity	
CTCAE Version 5.0 during a cycle of therapy	
Infections fall under many CTC terms	

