6.4 Concomitant medications

The investigator should instruct the subject to notify the study site about any new medications he/she takes after signing the informed consent. All medications including supplements and herbal/natural medications, surgeries, and significant non-drug therapies (including physical therapy and blood transfusions) taken within 30 days of screening and administered after the subject has signed informed consent must be listed on the appropriate eCRF.

For any antineoplastic therapy, surgery, or radiotherapy initiated after the start of study treatment, the reason for its use must be clearly documented and cancer recurrence must be assessed and documented.

Prior treatment for TB infection should be listed on the eCRF. Influenza vaccines administered two years prior to study start and pneumococcal vaccines administered five years prior to study start should be recorded on the eCRF. Vaccinations taken during the trial should also be reported on the eCRF. Subjects must be discontinued from the trial if administered any live and attenuated vaccines during the course of the study (see Section 6.4.2).

Confidential

Subjects who are on warfarin or warfarin like treatment with narrow therapeutic index should have their international normalized ratio (INR) measured locally and warfarin or warfarin like treatment dose adjusted accordingly within one month from starting study treatment. This is a general precautionary measure because canakinumab is not expected to interact with warfarin.

Drug-drug interaction potential

No formal drug-drug interaction studies have been conducted with canakinumab. Elimination pathways for IgG type monoclonal antibodies such as canakinumab are distinct from metabolic pathways of small molecules. The IgG-based molecules are cleared from the body by a combination of processes such as proteolysis by the liver, elimination by the Reticuloendothelial System and nonspecific endocytosis, whereas small molecular weight drugs are typically eliminated through CYP450-mediated oxidation pathways and are therefore not expected to affect the pharmacokinetics of canakinumab. The expression of hepatic CYP450 enzymes may be suppressed by the cytokines that stimulate chronic inflammation, such as IL-1 β . Thus, CYP450 expression may be normalized when potent cytokine inhibitory therapy, such as canakinumab is introduced.

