6.4.2.1 Immunosuppressants

Use of any treatments below is NOT allowed after the start of study treatment due to potential increase in immunosuppressant related concomitant conditions. They are prohibited for the duration of the study and for at least 130 days after discontinuation of study treatment.

If a subject chooses to continue one of the medications below, they would still be required to be followed as per protocol to assess for NSCLC disease recurrence.

- Any anti retro-virals and / or any biologic drugs targeting the immune system (e.g., TNFα blockers, anakinra, rituximab, abatacept, tocilizumab)
- immune modulating agent in doses with systemic effects e.g.:
 - i. Prednisone >20 mg (or equivalent) oral or intravenous daily for >14 days;
 - ii. Prednisone > 5 mg and \leq 20 mg (or equivalent) daily for > 30 days;
 - iii. Equivalent dose of methotrexate >15 mg weekly.
- Live or attenuated vaccines within 90 days of study treatment and after initiation of study drug. Subjects must be discontinued from the trial if administered any live or attenuated vaccine during the course of the study.

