7.1 Study flow and visit schedule

Table 7-1 lists all of the assessments and indicates with an "X", the visits when they are performed. Each treatment cycle is 21 days (the 21 day cycle length is fixed regardless of whether the dose of canakinumab is withheld). All visits are to be scheduled according to the appropriate number of calendar days from study drug administration on Cycle 1 Day 1. A visit window of +/- 1 day in Cycle 1 and +/- 3 days in Cycle 2 onwards through EOT and Safety follow up is allowed. For Post treatment surveillance and Survival follow up, visit windows of \pm 7 days will apply in years 2 and 3, and visit windows of \pm 21 days for years 4 and 5. Imaging evaluations may be performed \pm 14 days of the due date of the assessment during years 1-3 and \pm 21 days in years 4 and 5. Note: If treatment with canakinumab/placebo is withheld or discontinued at any time during the study, all study visits, safety and efficacy assessments should continue according to the appropriate number of calendar days from Cycle 1 Day 1 as per the schedule of assessments.

Imaging assessments are to continue regardless of starting a new antineoplastic therapy after discontinuation of study treatment, if the patient has not progressed from their NSCLC or been diagnosed with new lung primary. All data obtained from these assessments must be supported in the subject's source documentation.

Subjects who discontinue from study treatment are to return for the end of treatment visit as soon as possible, and attend the follow-up visits as indicated in the Assessment Schedule

Subjects who discontinue study treatment before completing the study, and those who withdraw from the study for any reason, should be scheduled for a visit as soon as possible, at which time all of the assessments listed for the final visit will be performed.

As per Section 2.7, during a public health emergency as declared by local or regional authorities i.e. pandemic, epidemic or natural disaster that limits or prevents on-site study visits, alternative

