- Non-compliance, as defined by missing any single dose greater than 42 days from the intended day of the next scheduled dose.
- Initiation of a new antineoplastic therapy

Subjects who become pregnant during the trial must be withdrawn (Section 8.4). Subjects who become pregnant must cease all tumor assessments regardless of whether or not they developed recurrence.

The appropriate personnel from the site and Novartis will assess whether study treatment should be discontinued for any subject whose treatment code has been broken inadvertently for any reason.

Discontinuation from study is when the subject permanently stops receiving the study treatment, and further protocol-required assessments or follow-up, for any reason.

If the subject agrees, a final evaluation at the time of the subject's study discontinuation should be made as detailed in the assessment table (refer to Table 7-1).

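### Protocol 6.3.1, 6.4 and 6.4.2.1 take subjects off the study or trial where only treatment should stop, which a site could read as ending follow-up (minor)

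*Protocol*

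**What the plan says.** Three sections use study-level wording:

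- Protocol 6.3.1, for an interruption of more than 42 days: "then the subject must be discontinued from the study".
- Protocol 6.4: "Subjects must be discontinued from the trial if administered any live and attenuated vaccines during the course of the study".
- Protocol 6.4.2.1: "Subjects must be discontinued from the trial if administered any live or attenuated vaccine during the course of the study".

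Study discontinuation is a defined term. The glossary has "Point/time when the subject permanently stops receiving the study treatment and further protocol required assessments or follow-up, for any reason", and 7.1.4 repeats it: "Discontinuation from study is when the subject permanently stops receiving the study treatment, and further protocol-required assessments or follow-up, for any reason". Discontinuation from study treatment is a separate glossary entry, under which follow-up goes on. Trial is not defined separately; reading it as study is natural.

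Other text points the opposite way. In 7.1.4 the list of reasons to stop treatment includes "Non-compliance, as defined by missing any single dose greater than 42 days from the intended day of the next scheduled dose". Section 6.3.1 itself refers to that list: "Permanent treatment discontinuation is mandatory for specific events indicated as such in Table 6-2 or listed in Section 7.1.4". When treatment is withheld or discontinued, 7.1 says that "all study visits, safety and efficacy assessments should continue according to the appropriate number of calendar days from Cycle 1 Day 1". Section 7.1.4 warns that stopping treatment is not automatic withdrawal from the study, and 7.1.6.2 continues 12-weekly survival contact for everyone who stops treatment.

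SAP 2.5.1 and 2.6.1 handle treatment discontinuation by treatment policy for DFS and OS.

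**The concern.** One event, a 42-day interruption, carries two mandatory consequences that cannot both be followed. Under 7.1.4 the drug stops and scans continue. Under the literal words of 6.3.1, read with the protocol's own definition, the scans and survival contacts stop too. The vaccine rule has the same wording problem, and the vaccine trigger does not appear in the 7.1.4 list that would settle it.

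A treatment-policy estimand needs outcome data after the drug stops. A subject taken off the study would be censored for DFS at the last adequate tumor assessment (SAP Table 2-5) and for OS at the last date known alive (SAP 2.6.1). That is an avoidable loss of follow-up in randomised subjects, for a reason tied to treatment rather than to consent.

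The distinction is not pedantic. Amendment 03 rearranged 7.1.4 to separate the two kinds of discontinuation and edited 6.3.1 as well, but the study-level phrase remains in 6.3.1. Long interruptions were also foreseeable: the SAP 2.3.2 list of COVID-19 deviations includes doses not given and interruptions beyond 84 days.

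**Working it through.** **Which subjects are exposed**

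| Case | Text that keeps follow-up | Left exposed |
|---|---|---|
| More than 42 days, study-related AE or abnormal laboratory value | The next sentence of 6.3.1 sends these subjects to 7.1.4 for follow-up | Little |
| More than 42 days, other reason (for example logistical or COVID-19) | 7.1, 7.1.4 and 7.1.6.2, against the 6.3.1 wording | Yes, at sites reading 6.3.1 literally |
| Live or attenuated vaccine | 6.4.2.1 requires recurrence follow-up for subjects who go on with a listed product, which fits a single vaccination poorly; 7.1 and 7.1.6.2 | Yes, at sites reading 6.4 or 6.4.2.1 literally |

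**Plan's own figure.** The Protocol 10.8 inputs are 1500 subjects over 30 months, placebo median DFS 48 months, HR 0.716 and 5% yearly dropout. With exponential times they give 392 expected DFS events at 41.7 months, against the stated 42. The two-look design gives 90.5% power with the futility stop applied, against the stated 90.4%. The inputs reproduce.

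**Chance of an unseen DFS event per removed subject**

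- Placebo hazard λ = ln 2 / 48 = 0.01444 per month; canakinumab 0.716 × 0.01444 = 0.01034.
- Dropout μ = −ln(0.95)/12 = 0.00427 per month; k = λ + μ.
- Removal at day 64 (Cycle 2 Day 1, day 22, plus 42; 2.07 months) or day 400 (Cycle 18 Day 1, day 358, plus 42; 13.1 months), taking Cycle 1 Day 1 as the randomisation day. The subject is event-free and under follow-up at removal.
- P = (λ/k)(1 − e^(−kf)), where f is the time from removal to cut-off. Averaged over f uniform on [a, b]: (λ/k)[1 − (e^(−ka) − e^(−kb))/(k(b − a))].

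Design accrual (30 months, cut-off at month 42):

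- Placebo, day 64: f runs from 9.93 to 39.93 and k = 0.01871. P = 0.772 × [1 − (0.830 − 0.474)/0.561] = 28.1%.
- Canakinumab, day 400: f runs from 0 to 28.9 and k = 0.01461. P = 0.708 × [1 − (1 − 0.656)/0.422] = 13.0%.

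Late enrollees are those randomised between 5 Feb 2020 (Amendment 02) and 7 Dec 2021, when screening ended (used as a stand-in for the last randomisation). That is 22.0 months. The cut-off is assumed 3 months later, the minimum follow-up in Protocol 10.8.

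| | Placebo, day 64 | Placebo, day 400 | Canakinumab, day 64 | Canakinumab, day 400 |
|---|---|---|---|---|
| Design accrual | 28.1% | 17.6% | 21.2% | 13.0% |
| Late enrollees | 15.0% | 8.0% | 11.1% | 5.8% |

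The late-enrollee day-400 figures apply only to those who reach day 400 before cut-off: (25.0 − 13.1)/22.0 = 54%. With the cut-off 5 months after the last randomisation, the late-enrollee range becomes about 7% to 17%.

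Per ten removed subjects, the extremes are 10 × 0.058 = 0.6 and 10 × 0.281 = 2.8 hidden DFS events, against a target of 392.

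**Effect on timing.** Suppose a share of subjects, not given in the documents, lost all follow-up at a uniform time in months 0 to 12. The 392nd event would then be expected at month 42.2 for a 2% share, 43.0 for 5% and 44.5 for 10%, instead of 41.7.

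**The case against.** The best defence is that this is a drafting slip whose intended meaning is clear. Section 6.3.1 refers to the 7.1.4 treatment-stop list. Its next sentence speaks of discontinuing the study and still requires follow-up of those subjects, so the phrase is used loosely there. The stopping reasons for follow-up in 4.1, 7.1.4, 7.1.6.2 and 7.2.1 name neither trigger. Where the protocol wants tumor assessments to cease, as in pregnancy, 7.1.4 says so outright. Nothing shows that any site acted on the literal words.

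Most of this stands, and it is why the point is minor. It does not remove the contradiction: the 6.3.1 safeguard is limited to study-related adverse events and laboratory values, and the 6.4.2.1 safeguard is worded for continued use of a product.

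A practical objection also stands. The close-out SAP reports that the primary endpoint was not met, and Protocol 4.3 ends OS follow-up in that case, so new wording can recover little in this trial.

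**Conclusion.** The point holds as a minor inconsistency, wrong as written, in three mandatory instructions. The likely intent is to stop treatment only; the risk is confined to sites that followed the literal text, mainly for interruptions for other reasons and for vaccinations.

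The percentages describe what is lost for each removed subject. They rest on exponential times, the design medians and dropout, uniform accrual and the assumed cut-offs. No total can be given, because no count is reported.

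A reader might infer more than the documents support:

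- **Follow-up was ordered to stop, or did stop.** Sections 7.1, 7.1.4 and 7.1.6.2 say otherwise, and no such removals are reported.
- **Bias or lost power.** Nothing indicates which arm would lose more subjects. The analyses are event-driven, so the nominal cost is time.
- **Table 6-2 has the same fault.** Its liver rows say only that the subject must be discontinued, but 6.3.1 and 7.1.4 identify the table's mandatory stops as discontinuation of treatment.
- **Subjects starting new antineoplastic therapy lose imaging.** One sentence of 7.1.4 leaves them out, but 7.1 and 7.2.1 continue their imaging, and the primary DFS analysis censors at NSCLC therapy in any case.

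**What to change.** In Protocol 6.3.1, 6.4 and 6.4.2.1, replace the study and trial wording with discontinuation from study treatment. Add in each place that recurrence imaging and survival follow-up continue per Table 7-1 unless consent is withdrawn.

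Where follow-up has already closed, do not resume visits. Report by arm the study discontinuations recorded for an interruption of more than 42 days or for a live or attenuated vaccine. That would show whether the wording cost any follow-up.

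Cost: a written amendment with sponsor and ethics approval, and health-authority approval where required (Protocol 12.1). The text changes in three sections, with no new visits. The report adds rows to the disposition table, which SAP 2.3.1 already presents by treatment with reasons and which the close-out SAP repeats as Table 2-1. Sample size, event targets, alpha and stated power do not change.

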	Permanently discontinue study treatment.
Concomitant elevations of AST or ALT and total bilir	ubin ^c
With normal baseline LFTs:	Interrupt study treatment. Assess if case is true DILI
Grade 2 ALT/AST (>3.0 x ULN) with bilirubin > 2.0 x ULN without evidence of cholestasis ^d (unless Gilbert's syndrome)	(Note: If total bilirubin > 3.0 x ULN is due to the indirect (non-conjugated) component only, and hemolysis as the etiology has been ruled out as per institutional guidelines (e.g., review of peripheral blood smear and haptoglobin determination), continue treatment at the discretion of the investigator.)
	If DILI confirmed - Permanently discontinue
	If Not DILI – interrupt treatment. Treat the identified cause according to institutional guidelines. Repeat LFTs within 48-72 hours, then monitor weekly, till enzyme levels resolve to ≤Grade 1 or Baseline.

-			
Co	ofida	entia	L
1,0		- III AI	

Dose Schedule modifications for Canakinumab ^a	
Worst toxicity	
CTCAE Version 5.0 during a cycle of therapy	
	Note: For additional information on follow-up of potential drug induced liver injury cases, refer to Section 6.3.3.2.
With abnormal baseline LFTs: ALT or AST >2 x baseline OR ALT or AST >8 x ULN (whichever is lower) combined with total bilirubin >2.0x ULN	After recovery, re-administration of study treatment could be considered only if Investigator assesses benefit to outweigh the risk. Note: For additional information on follow-up of potential drug induced liver injury cases, refer to Section 6.3.3.2.
Investigation (metabolic)	
Asymptomatic amylase and/or lipase elevation	
Grade 1 (> ULN - 1.5 x ULN)	May maintain dose level
Grade 2 (> 1.5 - 2.0 x ULN; > 2.0 -5.0 X ULN and asymptomatic)	May maintain dose level
Grade 3* (> 2.0 - 5.0 x ULN with signs or symptoms; > 5.0 ULN and asymptomatic)	Recommendation: Omit dose : If resolved to grade ≤ 1 or baseline in ≤ 7 days, then maintain dose level If resolved to grade ≤ 1 or baseline in > 7 days, then discontinue subject from study medication (mandatory)
Grade 4* (> 5.0 x ULN and with signs or symptoms)	Mandatory: Discontinue subject from study drug treatment.
*Note: A CT scan or other imaging study to assess the pa amylase and/or lipase. If asymptomatic Grade 2 elevation from study treatment.	ncreas, liver, and gallbladder must be performed within 2 weeks of the first occurrence of any ≥ Grade 3 of s of lipase and/or amylase occur again after restarting therapy, subjects will be discontinued permanently

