Vascular disorders	
Hypertension	
CTCAE Grade 3	Recommendation: Omit dose until resolved ≤ Grade 1, then maintain level
CTCAE Grade 4	Mandatory: Discontinue subject from study drug treatment
Gastrointestinal	
Pancreatitis	
Grade 2	Recommendation: Maintain dose level
Grade ≥ 3	Mandatory: Discontinue subject from study drug treatment

Novartis

Amended Protocol Version 03 (Clean)

Daga Cabadula madifications for Construmenta	
Dose Schedule modifications for Canakinumab ^a Worst toxicity	
CTCAE Version 5.0 during a cycle of therapy	
Diarrhea	
	he first sign of abdominal cramping, loose stools or overt diarrhea
Grade 1	May maintain dose level but initiate anti-diarrhea treatment
Grade 2	Recommendation: Omit dose until resolved to \leq Grade 1, then maintain dose level.
Grade 3	Recommendation: Discontinue subject from study drug treatment
Grade 4	Mandatory: Discontinue subject from study drug treatment
Skin and subcutaneous tissue disorders	
Rash/photosensitivity	
Grade 1	May maintain dose level. Consider to initiate/institute appropriate skin toxicity therapy (such as antihistamines and/or topical corticosteroids)
Grade 2	May maintain dose level, but initiate/intensify appropriate skin toxicity therapy (such as antihistamines and/or topical corticosteroids).
Grade 3, despite skin toxicity therapy	Recommendation: Omit dose until resolved to Grade ≤ 1, then:
	If resolved resolved in \leq 7 days, then maintain dose level
	If resolved resolved in > 7 days (despite appropriate skin toxicity therapy), then discontinue subject from study drug treatment (mandatory)
Grade 4, despite skin toxicity therapy	Mandatory: Discontinue subject from study drug treament
Fatigue/ Asthenia (General disorders and administra	
Grade 1 or 2	May maintain dose level
Grade 3	Recommendation: Omit dose until resolved to ≤ grade 1, then :
	If resolved in \leq 14 days, then maintain dose level
	If resolved in > 14 days, then discontinue subject from study drug treatment (mandatory)
Other adverse events	
Grade 1 or 2	May maintain dose level
Grade 3	Recommendation: Omit dose until resolved to ≤ grade 1, maintain dose level
Grade 4, except alopecia	Recommendation: Discontinue from study drug treatment

Novartis Amended Protocol Version 03 (Clean)

Page 66 of 144 Protocol No. CACZ885T2301

Dose Schedule modifications for Canakinumab^a

Worst toxicity

CTCAE Version 5.0 during a cycle of therapy

All dose modifications should be based on the worst preceding toxicity.

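### Table 6-2 makes a recurrent asymptomatic Grade 2 amylase/lipase rise a mandatory stop but sets no stop for a recurrent Grade 3 rise that clears within 7 days

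*Protocol*

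**What the plan says.** All of this is in Protocol Section 6.3.1, Table 6-2, in the block on amylase and lipase.

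- **Grade 2 row.** Defined as "Grade 2 (> 1.5 - 2.0 x ULN; > 2.0 -5.0 X ULN and asymptomatic". Dosing may continue; no hold is called for.
- **Grade 3 row.** Defined as "Grade 3* (> 2.0 - 5.0 x ULN with signs or symptoms; > 5.0 ULN and asymptomatic". The recommendation is to omit the dose, with two branches: "If resolved to grade ≤ 1 or baseline in ≤ 7 days, then maintain dose level", and "If resolved to grade ≤ 1 or baseline in > 7 days, then discontinue subject from study medication (mandatory". Neither branch is limited to a first episode.
- **Grade 4 row** (above 5.0 x ULN with signs or symptoms). Discontinuation is mandatory.
- **Note**, flagged by an asterisk on the Grade 3 and Grade 4 rows only. Its first sentence requires imaging of the pancreas, liver and gallbladder, which "must be performed within 2 weeks of the first occurrence of any ≥ Grade 3 of" either enzyme. Its second sentence takes asymptomatic Grade 2 elevations as its subject and says that if these elevations of "lipase and/or amylase occur again after restarting therapy, subjects will be discontinued permanently".

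Two general statements frame the table. Section 6.3.1 says: "Permanent treatment discontinuation is mandatory for specific events indicated as such in Table 6-2 or listed in Section 7.1.4". The table closes with: "All dose modifications should be based on the worst preceding toxicity".

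**The concern.** A recurrence rule should not become more lenient as the event becomes worse. Here the note ends treatment for a recurrent asymptomatic Grade 2 rise however fast it clears, while a recurrent Grade 3 rise that clears in a week may be followed by another dose, with no limit on the number of episodes. What is at stake is the safety and clarity of a mandatory stopping rule. A site that follows the text literally would stop the subject with the smaller enzyme rise and could keep treating the one with the larger rise. The layout adds to the difficulty, because the Grade 2 row carries no asterisk to warn that a note can end treatment at that grade.

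**Working it through.** The plan states no figure on this point, so the check is a reading of the rules side by side.

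**Step 1. Outcome for a rise that occurs after a restart.** The values are illustrative, chosen to fall inside the table's own grade limits. The two Grade 3 cases are split by time to return to Grade 1 or below, or to baseline.

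| Case | Value | Grade | Time to clear | Governing text | Outcome |
|---|---|---|---|---|---|
| 1 | 1.6 x ULN, no symptoms | 2 | any | note | permanent stop |
| 2 | 3.0 x ULN, no symptoms | 2 | any | note | permanent stop |
| 3a | 3.0 x ULN, symptoms | 3 | 7 days or less | Grade 3 row | may resume |
| 3b | 3.0 x ULN, symptoms | 3 | over 7 days | Grade 3 row | mandatory stop |
| 4a | 6.0 x ULN, no symptoms | 3 | 7 days or less | Grade 3 row | may resume |
| 4b | 6.0 x ULN, no symptoms | 3 | over 7 days | Grade 3 row | mandatory stop |
| 5 | 6.0 x ULN, symptoms | 4 | any | Grade 4 row | mandatory stop |

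Stops: 1, 2, 3b, 4b and 5, which is 5 of 7. May resume: 3a and 4a, which is 2 of 7. Both that may resume are of higher grade than cases 1 and 2, which must stop. The count shows the logic of the rule and carries no frequencies.

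**Step 2. Does any other rule close the gap?**

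- Section 6.3.1 makes permanent discontinuation mandatory for events that the table or Section 7.1.4 marks as such. Neither marks a recurrent Grade 3 enzyme rise that clears in 7 days.
- The Section 7.1.4 list adds pregnancy, sponsor termination, subject or physician decision, non-compliance and new antineoplastic therapy. None is an enzyme rule.
- The worst-preceding-toxicity instruction sends a recurrent Grade 3 rise to the Grade 3 row, which is the row that allows resumption.
- The 42-day interruption limit (Sections 6.3.1 and 7.1.4) does not reach an event that clears in 7 days or less.

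**Step 3. What does occurring again mean?** It could mean a Grade 2 value appearing after a Grade 3 hold, or a second Grade 2 rise. Grade 2 has no hold and Grade 4 has no restart, so within this block a restart most naturally follows a Grade 3 hold. On the narrower reading the inversion still holds for any subject who had an earlier Grade 2 value.

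**Step 4. How wide is the branch?** If the restart followed a Grade 3 enzyme hold, the first rise must already have cleared in 7 days or less, since otherwise treatment would have ended. The second must do so too. Scheduled chemistry comes once per 21-day cycle (Section 7.1 and Table 7-1), so each clearance would ordinarily need an unscheduled draw to be seen in time.

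**The case against.** The strongest reply is that open-ended Grade 3 restarts are how Table 6-2 is built. Thrombocytopenia and rash at Grade 3 use the same 7-day split, fatigue uses a 14-day split, and neutropenia and hypertension at Grade 3 resume after resolution, all without an episode limit. On that view the Grade 2 sentence is the outlier, and deleting it would also restore order. The description of the other rows is right. It does not remove the problem, because only this block pairs such a restart with a mandatory stop for a lower-grade recurrence. Between the two repairs, extending the stop is the one that favours subject safety.

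A second reply is that Grade 2 must mean Grade 2 or worse. The same note writes a greater-or-equal sign where it means a threshold, and the Grade 3 row gives its own instruction for this event, so the text does not carry that reading.

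A third is that the block is headed as asymptomatic, so case 3a should not count. The rows do include symptomatic values. Even with case 3a set aside, case 4a against case 2 shows the same inversion among asymptomatic rises.

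Several limiting points stand in full. The Grade 3 hold is a recommendation. Keeping the dose level fixes the dose and does not oblige anyone to re-dose. Section 7.1.4 lets the investigator stop treatment judged detrimental.

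A reader might infer that the protocol requires repeated dosing through Grade 3 toxicity, or leaves the pancreas unexamined because the extra imaging is tied to a first episode. The documents do not support either. Resumption is only permitted, and CT or MRI of chest, abdomen and pelvis is mandated every 12 weeks in year one (Section 7.2.1). Nor do they show that sites actually handled such cases differently.

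**Conclusion.** The rule is wrong as written, at low severity. In the fast-clearing branch it is stricter for the milder recurrence, and nothing elsewhere in the protocol corrects this.

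The effect is narrow. Grade 4 rises, Grade 3 rises that take more than 7 days to clear, and pancreatitis of Grade 3 or above are already mandatory stops. The number of subjects affected is probably small, but that is a judgement: the documents give no incidence of Grade 3 enzyme rises. Power, alpha and the primary analysis are untouched, so it would be a mistake to read this as a threat to the trial's results.

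The conclusion rests on a literal reading of the table. It also takes the note's second sentence, which the text extraction splits across columns, as rejoined. The halves fit without a gap, and the restriction to Grade 2 is in the text.

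**What to change.** Replace the second sentence of the note with: *If an asymptomatic Grade 2 elevation, or any Grade 3 elevation, of lipase and/or amylase occurs after study treatment has been restarted following a Grade 3 amylase/lipase hold, the subject will be discontinued permanently from study treatment.* Put the note's asterisk on the Grade 2 row as well. This adds no imaging at Grade 2, because the imaging sentence carries its own Grade 3 threshold.

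For a restart after a Grade 3 enzyme hold, cases 3a and 4a then become stops, so 5 + 2 = 7 of 7 end treatment. The 7-day branch remains for a Grade 3 rise before such a restart. The wording also settles which restart is meant. If the sponsor intends the rule to follow a restart for any reason, the sentence should say so. It deliberately leaves out a symptomatic Grade 2 value between 1.5 and 2.0 x ULN, which the present note does not name and which the Grade 3 inversion does not require.

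The cost is one sentence and one asterisk, by amendment or clarification letter. A few subjects whose second Grade 3 rise clears quickly would stop study drug. Timing limits the practical gain: Amendment 03 records that screening ended in December 2021, treatment lasts about 54 weeks, and the close-out SAP has a cut-off of 7 February 2023. The correction is therefore mainly to the rule itself, and to any later protocol that reuses this table.
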